1.4 Role of the CDK4/6 pathway in breast cancer

Cell cycle progression is directly regulated by cyclin-dependent serine-threonine protein kinases (CDKs). Extracellular growth and adhesion signals increase the level and function of cyclin D proteins within the cell. In turn, the cyclin D proteins associate with and activate CDK4 and CDK6 (1). CDK4 and CDK6 phosphorylation leads to inactivation of the retinoblastoma protein (pRb) and thus releases E2F which in turn leads to the transcription initiation of proteins involved in cell cycle propagation and cell proliferation. The luminal A and B subtypes of breast cancer (85% of which are ER+/HER2-negative) have high rates of cyclin D/CDK activation; in the luminal A and B subtypes, cyclin D1 (CCND1) amplifications were observed in 29% and 58%, and CDK4 amplifications were observed in 14% and 25% respectively (5, 9).

Luminal A subtype tumors also have loss of CDKN2A, which encodes p16Ink4a, a CDK inhibitor (12). The luminal subtypes also maintain expression of Rb, which is essential for benefit from treatment with a CDK4/6 inhibitor (4). Dysregulation of cell cycle checkpoints is common in cancer. Modulating the cell cycle has always been an attractive therapeutic target in cancer, and previously published data have suggested that CDK4/6 inhibition may play a key role in the treatment of subsets of breast cancers. Patients with HR+ breast cancer exhibiting a gene expression signature of Rb loss had shorter recurrence-free survival following adjuvant tamoxifen (13). A tumor gene expression signature of E2F activation was associated with higher residual tumor cell proliferation following pre-surgical AI therapy. Therefore, activation of the CDK4/CDK6/E2F axis promotes endocrine resistance, and treatment with a CDK4/6 inhibitor or knockdown of CDK4 expression abrogates endocrine-resistant cell proliferation. In conclusion, loss of cell cycle control is a hallmark of cancer, and aberrations in the cyclin/CDK/Rb pathway are common in breast cancer. Consequently, inhibition of this pathway (at the level of CDK4/6)

leads to reactivation of Rb and binding of E2F, thus leading to cell cycle arrest. Therefore, targeting the inhibition of this pathway is considered an attractive therapeutic strategy. Additionally, preclinical and clinical data demonstrate that CDK4/6 inhibitors are active in advanced HR+ breast cancer. Palbociclib (PD 0332991) is a selective inhibitor of CDK4/6 that inhibits proliferation and induces apoptosis in preclinical models of endocrine-resistant breast cancer (4, 11). Preclinical data with palbociclib demonstrated synergy with tamoxifen in ER+ breast cancer cell lines; moreover, palbociclib enhanced sensitivity to tamoxifen in cell lines with conditioned resistance to ER blockade (6).

2 INTRODUCTION TO INVESTIGATIONAL TREATMENT(S) AND OTHER STUDY TREATMENT(S)

This study includes RIBOCICLIB, Tamoxifen, and Goserelin (if indicated)

2.1 Overview of RIBOCICLIB

[figure not shown]
The ribociclib drug product is planned for oral administration. The available clinical forms are 10 mg, 50 mg and 200 mg hard gelatin capsules/tablets. The capsules only contain the drug substance; there are no excipients.

Ribociclib should be administered as a flat-fixed dose (400 mg or 600 mg daily), and not by body weight or body surface area.

Patients should be instructed to return unused study drugs to the site at discontinuation or completion of treatment. The site personnel will ensure that the appropriate dose of each study drug is administered and that the drug accountability is performed.

In order to minimize the inter-patient variability of PK assessments, ribociclib should be taken as follows:

- Patients should be instructed to take the ribociclib capsules with a large glass of water (~250 ml) at the same time each morning.
- Patients can take meals with their study treatment.

- Based on these data, ribociclib can be taken without regard to meals. Patients should be instructed to swallow the ribociclib capsules whole and not to chew, crush or open them.
- If vomiting occurs during the course of treatment, no re-dosing of the patient is allowed before the next scheduled dose
- Any doses that are missed (not taken within 6 hours of the intended time) should be skipped and should not be replaced or made up on a subsequent day.
- Patients must avoid consumption of grapefruit, Seville oranges or products containing the juice of each during the entire study and preferably 7 days before the first dose of study medications, due to potential CYP3A4 interaction with the study medications. Orange juice is allowed.

2.1.1 Nonclinical pharmacokinetics and metabolism

[figure not shown]
The pharmacokinetics (PK) of ribociclib was investigated in mouse, rat, dog and monkey. The absorption of ribociclib after oral administration was moderate for rats (48-84%). Oral bioavailability (BA) ranged between 10% and 65% across animal species. Time to maximum plasma drug concentration (Tmax) was between 2 and 4 hours. Terminal half-life (T1/2) of ribociclib was moderate in rodents and monkeys (~2-5 hours), and was longer in dogs (18 hours). Ribociclib is moderately bound to plasma proteins in all animal species with unbound fractions in plasma (fu) ranging from 20-34% (human fu = 30%). [3H] Ribociclib and metabolites were extensively distributed to tissues in male rats, but there was no uptake into the brain.

A solid black horizontal bar at the bottom of the page, likely a placeholder for a footer or a decorative element.

113

[REDACTED]

[REDACTED]

[REDACTED] [REDACTED]

[REDACTED]

[REDACTED]

2.2 Overview of Tamoxifen

Tamoxifen has been used for over 30 years to treat both pre- and postmenopausal women with HR+ breast cancer. Its antitumor effects are thought to be due to its anti-estrogenic activity, mediated by competitive inhibition of estrogen

binding to ER (15). Adjuvant therapy with Tamoxifen for 5 years resulted in a 34% reduction in the annual breast cancer death rate, with an absolute reduction in mortality of 9.2% at 15 years (16).

The recommended dose for treatment of breast cancer is 20 mg daily (17). Tamoxifen is generally well tolerated and side effects are mainly attributable to estrogen deprivation. However, in some tissues, Tamoxifen acts as an estrogen agonist, and these estrogenic effects may be beneficial or detrimental, depending on the target organ. For example, tamoxifen has favorable effects on bone health, lipid metabolism and the cardiovascular system, but long-term tamoxifen use is also associated with serious, potentially life-threatening adverse events, including invasive endometrial cancer and thromboembolic disease (18).

Following oral administration of a single dose of Tamoxifen (20 mg), Tmax was achieved approximately 5 hours post-dose and concentrations declined with a terminal elimination T1/2 of approximately 5-7 days. Steady-state is achieved for Tamoxifen in approximately 4 weeks, while for its metabolite, N-desmethyltamoxifen, steady-state is achieved in approximately 8 weeks (17). Tamoxifen metabolism is complex and extensive after oral administration. Tamoxifen is a substrate of CYP3A4/5, CYP2D6, and CYP2C9 and an inhibitor of P-glycoprotein (P-gp) (17). Tamoxifen is predominantly metabolized by CYP3A4/5 to N-desmethyltamoxifen. A minor route of metabolism occurs via CYP2D6 to form the pharmacologically active metabolite, 4-hydroxytamoxifen. These metabolites are further metabolized to several secondary metabolites, one of which is the pharmacologically active metabolite, 4-hydroxydesmethyltamoxifen (endoxifen), formed mainly via CYP2D6 from N-desmethyltamoxifen. The two pharmacologically active metabolites, 4-hydroxytamoxifen and endoxifen, are 30- to 100-fold more potent than tamoxifen in terms of ER binding affinity and effects on breast cancer cell proliferation and gene expression (19). In breast cancer patients, endoxifen plasma concentrations are 5- to 10-fold higher than 4-hydroxytamoxifen (20, 21), suggesting that endoxifen may contribute significantly to the overall response to tamoxifen therapy. However, it is also likely that the combined pharmacologic activity of tamoxifen and its active metabolites contribute to the clinical efficacy of tamoxifen (19).

Formation of the pharmacologically active metabolites (4-hydroxytamoxifen and endoxifen) occurs predominantly through CYP2D6 (21). Reduced CYP2D6 activity, either through genetic polymorphisms of the enzyme or through concomitant administration of drugs that are CYP2D6 inhibitors, could lead to reduced exposure to endoxifen (21, 22). In addition, inhibition or induction of CYP3A4 may affect the metabolism of tamoxifen. Based on the prescribing information of tamoxifen, no dose adjustment is required for CYP2D6 poor metabolizers or for individuals taking medications that are strong inhibitors or inducers of CYP3A4. CYP2D6 poor metabolizer status has been associated with poorer invasive disease-free survival in tamoxifen treated patients in a number of studies, though not in others (23). The value of CYP2D6 genotyping in tamoxifen therapy is therefore still under investigation and is not standard of care. For information on tamoxifen and management of potential tamoxifen related adverse events refer to the Tamoxifen SmPC or Prescribing Information.

2.3 Potential for a drug-drug interaction between Ribociclib and Tamoxifen

The prescribing information for Tamoxifen suggests that Tamoxifen may affect the metabolism of co-administered drugs. A significant increase in anticoagulant effect may occur when Tamoxifen is co-administered with coumarin-type

anticoagulants. These medications should be avoided if possible, otherwise careful monitoring of prothrombin time is recommended. In addition, tamoxifen has been shown to reduce letrozole plasma concentrations following coadministration (17).

Tamoxifen could potentially affect the metabolism of co-administered drugs that are substrates for CYP3A4 since *in vitro* data indicate tamoxifen is a reversible and time-dependent inhibitor of CYP3A4 (24) as well as an inducer of CYP3A4 (25). Ribociclib is mainly metabolized by CYP3A4 with a minor contribution by FMO3 based on *in vitro* data. Clinical drug interactions studies of tamoxifen and drugs that are mainly metabolized by CYP3A4 (e.g., gefitinib, palbociclib) resulted in no significant changes in exposure in the presence of steady-state levels of Tamoxifen when compared with exposures when given alone (26, 27). Therefore, based on these *in vivo* data, Tamoxifen is not expected to affect ribociclib PK due to CYP-mediated interactions. Tamoxifen is also an inhibitor of P-gp (17) and could potentially affect substrates of this transporter. However, since ribociclib is a low-affinity substrate of P-gp with moderate permeability, ribociclib PK is not expected to be significantly affected by inhibition of P-gp by Tamoxifen.

Ribociclib may increase the exposure of co-administered drugs that are substrates for CYP3A4 due to time-dependent inhibition of the enzyme. *In vitro* studies indicate ribociclib is a reversible ($K_i = 35 \mu\text{M}$) and time-dependent inhibitor ($KI = 5.06 \mu\text{M}$, $kinact = 0.0245 \text{ min}^{-1}$) of CYP3A4. Tamoxifen is a substrate of CYP3A4/5, CYP2D6, and CYP2C9 (28). *In vitro*, troleandomycin and ketoconazole (CYP3A4 inhibitors) reduced the formation of N-desmethyltamoxifen (21); however the clinical significance is unknown. No clinical studies have been conducted to evaluate the effect of a strong inhibitor of CYP3A4/5 on the PK of Tamoxifen. However, the effect of coadministration of strong CYP3A4/5 inducers (e.g., rifampicin, aminoglutethimide) with tamoxifen has been evaluated and resulted in reduced concentrations of Tamoxifen and its metabolites (20, 29). Based on this information, a potential DDI with coadministration of ribociclib cannot be fully excluded.

2.4 Overview of goserelin

Goserelin (Zoladex®) is a synthetic decapeptide analog of gonadotropin releasing hormone (GnRH) indicated for prostatic carcinoma, endometriosis, endometrial thinning, and advanced breast cancer. Goserelin is administered subcutaneously every 28 days at a dose of 3.6 mg. Following subcutaneous administration of goserelin (3.6 mg for 2 months), T_{max} was 12-15 days post-dose in males and 8-22 days post-dose in females. The metabolism of goserelin is not CYP-mediated; rather it is metabolized by hydrolysis of C-terminal amino acids. More than 90% of a radiolabeled dose was excreted in the urine, with approximately 20% of the dose in urine accounted for by unchanged goserelin. The adverse events occurring in > 20% of women included hot flushes, headache, sweating, acne, emotional lability, depression, decreased libido, vaginitis, breast atrophy, seborrhea and peripheral edema (30).

For information on goserelin and management of goserelin related adverse events refer to the Zoladex® SmPC or Prescribing Information.

2.4.1 Very Low potential for drug-drug interactions with goserelin

The metabolism of goserelin is not CYP-mediated; rather hydrolysis of C-terminal amino acids is the major clearance mechanism. No formal clinical DDI studies have been conducted or reported with Goserelin and has been combined with Tamoxifen as SOC. Based on the available information, goserelin is not expected to affect the metabolism of nor be affected by co-administered drugs (30).

2.5 Rationale for the combination of CDK4/6 inhibitors with Tamoxifen plus goserelin

Data from The Cancer Genome Atlas highlight the importance of the Cyclin/CDK/Rb pathway in breast cancer (2, 3). Abnormalities that result in CDK activation are highly enriched in the luminal A and B molecularly defined subgroups, ~85% of which were ER+/Her2- (5). Cyclin D1 amplifications were observed in 29% and 58% of the luminal A and B subtypes, respectively, and CDK4 amplifications were observed in 14% and 25% of luminal A and B subtypes, respectively. Luminal A subtype tumors also have loss of CDKN2C, which encodes p16Ink4a, a CDK inhibitor. The luminal subtypes also maintain expression of Rb, which would be essential for benefit from treatment with a CDK4/6 inhibitor (2-4). PD0332991 is an oral, potent, selective inhibitor of CDK4/6 that was shown to inhibit proliferation and induce apoptosis in multiple preclinical models of endocrine-resistant breast cancer, both *in vitro* and *in vivo* (4, 11). In the clinic, PD0332991 was studied in a randomized Phase II study in combination with the non-steroidal aromatase inhibitor letrozole. This combination significantly prolonged median progression free survival in postmenopausal women with locally recurrent or advanced ER+/HER2- breast cancer treated in the front-line setting (median PFS 26.1 vs 7.5 months, reported in Finn et al (6).

Most breast tumors that initially respond to anti-estrogen therapy acquire resistance in time. Given the above pre-clinical data, there may be benefit from a combination of Tamoxifen and RIBOCICLIB, in women with hormone sensitive tumors as well as those whose tumors became unresponsive. Current and recently completed studies restrict CDK trials and limit the patient population to only postmenopausal patients but it is well known that younger, pre-menopausal and perimenopausal patients often have more “aggressive” disease and more endocrine-resistant disease and this combination may be very helpful in delaying endocrine resistance in this patient population. Multiple adjuvant studies have described amenorrhea as a positive prognostic factor in patients with overall survival after adjuvant chemotherapy. Based upon these studies, the NCCN guidelines recommend goserelin to be strongly considered in premenopausal women who are menstruating despite receiving chemotherapy (7).

In a retrospective study done at one hospital, over 150 patients with stage Ia to IIIa ER + breast cancer who received goserelin or chemotherapy were reviewed. Survival analysis was assessed by the Kaplan-Meier method. Survival at 11 years was significantly better in the goserelin group ($P < 0.0012$). The lifetime lost was lower in the goserelin group (42 months vs. 66 months). The quality adjusted survival (QAS) of patients who received goserelin was longer (122.5 ± 6.3 vs. 112.2 ± 6.7 months). The quality-adjusted life-year was higher in the goserelin group. Goserelin therapy results in better survival and higher utility-weighted life-years, and is more cost-effective (8). We plan to add goserelin to all women who are not postmenopausal. We estimate that of the 40 patients on study, approximately 20 patients will be post-

menopausal and 20 will not meet the standard criteria of a post-menopausal state (no menstrual cycles for greater than 12 months and FSH of ≥ 40).

3 OBJECTIVES

3.1 Primary Objective

Phase I - Confirm DLT:

The phase I portion of the study is a dose escalation to confirm the safety of the combination and to determine the DLT and the RP2D for ribociclib with Tamoxifen.

Phase Ib Dose Expansion:

Our goal is to further evaluate their safety in adult patients with ER+/HER2- locally advanced or metastatic breast cancer. Phase I trials are increasingly including dose-expansion cohorts after the maximum-tolerated dose (MTD) has been reached to better characterize the toxicity profile or identify early signs of efficacy within a specific disease population. We will evaluate two cohorts in the phase I expansion. The first will be the standard 21 days of ribociclib dosing with 7 days rest period and the second will be the continuous dosing (daily). Tamoxifen, per SOC, will be dosed daily in both cohorts. We will attempt to assess the anti-tumor activity ribociclib + Tamoxifen.

3.2 Secondary Objectives:

- Time to progression
- Overall survival from study initiation at 6 months, 12 months, 18 months and 24 months.
- Pre-treatment and post-treatment ER receptor expression in tumor in those patients who volunteer for optional tissue evaluation.
- **Pharmacokinetics** in the dose escalation as well as the dose expansion arms.

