- a. Toxicity assessment must be performed until all treatment-related toxicities have been resolved or decreased to grade 1. Adverse events must be recorded up to 30 days after termination on study.
- b. PKs to be collected at C3D15 and C3D16 for steady state evaluation at 7 time points: Pre-dose, 0.5 hr post dose, 1 hr post dose, 2 Hrs post-dose, 4 Hrs Post dose, 8 hours post dose, 24 hours post dose.
- c. Tests done within 28 days can be used for baseline eligibility.
- d. Tumor Biopsy is optional. Baseline tumor biopsy for predictive markers (optional) if accessible, if not accessible based on surgical evaluation, then archival tissue from metastatic site allowed). Baseline tumor sample will be collected at screening, or following progression on prior treatment and prior to C1D1. A newly obtained post-progression tumor sample for resistance is optional. Should patient agree, it will be collected at time of progression and before a new treatment is initiated.
- e. Biomarkers to be collected include: CTC, CEA, Ca15-3, Ca 125, Ca 27-29/ (If clinically indicated) at time of restaging scans. Further biomarker testing for exploratory circulating tumor DNA will be collected predose on C1D1, predose C3D1, Predose C5D1, and C7D1. Biomarkers will also be collected at EOT, or within 15 days of the last dose.
- f. for women of childbearing potential. Pregnancy test will be repeated if clinically indicated.
- g. Thirty day follow up to occur after last dose of study drug. Used for either end of treatment or study completion. Includes resolution of serious adverse events and adverse events related to study treatment.
- h. Disease assessment is determined at visit every 8 weeks after staging scans and tumor marker collection
- i. EKG to be done in triplicate. Two minutes apart, after patient has been resting for 5-10 minutes
- j. Baseline CMP to include magnesium and phosphorous level for screening criteria.
- k. Female participants only

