8.7 Treatment Duration

Eligible patients will receive treatment as described above, in consecutive 4-week cycles, until progression of disease or unacceptable toxicity. Patients are expected to receive treatment for at least 2 cycles, at which time the first evaluation for efficacy will occur. If there is continued safety and tolerability in the absence of any documented disease progression, treatment may continue for 2 years or until progression or non-tolerance.

Patients will be followed for evaluation of safety for at least 30 days after the last dose of study drug. Any study drug-related serious adverse events will be followed until resolution, return to baseline grade, or deemed irreversible by the Investigator.

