11.3 Evaluation of Best Overall Response

The best overall response is the best response recorded from the start of the treatment until disease progression/recurrence (taking as reference for progressive disease the smallest measurements recorded since the treatment started). In general, the patient's best response assignment will depend on the achievement of both measurement and confirmation criteria.

Note:

- Patients with a global deterioration of health status requiring discontinuation of treatment without objective evidence of disease progression at that time should be reported as "symptomatic deterioration". Every effort should be made to document the objective progression even after discontinuation of treatment.
- The best overall response for an early death, i.e., a patient who dies without documentation of disease progression and before it was time to conduct the first tumor reassessment, will be considered unevaluable or not assessed adequately. Response will also be considered unevaluable for any patient receiving treatment (regardless of how much was received) who did not have any follow-up assessment completed before initiation of alternative treatment. These patients must be replaced in both the phase I portion and the phase Ib expansion.
- In some circumstances, it may be difficult to distinguish residual disease from normal tissue. When the evaluation of complete response depends upon this determination, it is recommended that the residual lesion be imaged by PET scan or be investigated by fine needle aspirate/biopsy before confirming the complete response status.

Target Lesions	Non-target Lesions	New Lesions	Overall Response
CR	CR	No	CR
CR	Non-CR/Non-PD	No	PR
PR	Non-PD	No	PR
SD	Non-PD	No	SD
PD	Any	Yes or No	PD
Any	PD	Yes or No	PD
Any	Any	Yes	PD

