12.1 Adverse Event Characteristics

- **CTCAE term (AE description) and grade:** The descriptions and grading scales found in the revised NCI Common Terminology Criteria for Adverse Events (CTCAE) version 4.03 is utilized for AE reporting. All appropriate treatment areas should have access to a copy of the CTCAE version 4.03. A copy of the CTCAE version 4.03 can be downloaded from the CTEP web site (<http://ctep.cancer.gov>).
- **‘Expectedness’:** AEs can be ‘Unexpected’ or ‘Expected’ for expedited reporting purposes only
- **Attribution** of the AE:
 - Definite – The AE is *clearly related* to the study treatment.
 - Probable – The AE is *likely related* to the study treatment.
 - Possible – The AE *may be related* to the study treatment.
 - Unlikely – The AE is *doubtfully related* to the study treatment.
 - Unrelated – The AE is *clearly NOT related* to the study treatment.

12.2 Investigator Reporting: Novartis instructions for rapid notification of serious adverse events

All serious adverse events must be reported to Novartis Pharmaceuticals Drug Safety and Epidemiology Department (DS&E) and reporting will be done via the Investigators or his/her designee.

All events must be reported, by FAX [REDACTED] to Novartis Pharmaceuticals DS&E Department within 24 hours of learning of its occurrence. This includes all serious, related, not related, labeled (expected) and unlabeled (unexpected) adverse experiences.

All deaths during treatment or within 30 days following completion of active protocol therapy must be reported within 24 hours.

Any serious adverse event occurring after the patient has provided informed consent and until 4 weeks after the patient has stopped study participation must be reported. This includes the period in which the study protocol interferes with the standard medical treatment given to a patient (e.g. treatment withdrawal during washout period, change in treatment to a fixed dose of concomitant medication).

Serious adverse events occurring more than 4 weeks after study discontinuation need only be reported if a relationship to the Novartis study drug (or therapy) is suspected.

For Comparator Drugs/Secondary Suspects (Concomitant Medications), all serious adverse experiences will be forwarded to the product manufacturer by the investigator.

Pregnancies

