13 DATA SAFETY MONITORING

Adverse events

Definitions and reporting

An adverse event is defined as the appearance of (or worsening of any pre-existing) undesirable sign(s), symptom(s), or medical condition(s) that occur after patient's signed informed consent has been obtained.

Abnormal laboratory values or test results occurring after informed consent constitute adverse events only if they induce clinical signs or symptoms, are considered clinically significant, require therapy (e.g., hematologic abnormality that requires transfusion or hematological stem cell support), or require changes in study medication(s).

Adverse events that begin or worsen after informed consent should be recorded in the Adverse Events CRF. Conditions that were already present at the time of informed consent should be recorded in the Medical History page of the patient's CRF. Adverse event monitoring should be continued for at least 30 days (or 5 half-lives, whichever is longer) following the last dose of study treatment. Adverse events (including lab abnormalities that constitute AEs) should be described using a diagnosis whenever possible, rather than individual underlying signs and symptoms. When a clear diagnosis cannot be identified, each sign or symptom should be reported as a separate Adverse Event.

Adverse events will be assessed according to the Common Terminology Criteria for Adverse Events (CTCAE) version 4.03. If CTCAE grading does not exist for an adverse event, **the severity of mild, moderate, severe, and life-threatening, corresponding to Grades 1 - 4, will be used.**

The occurrence of adverse events should be sought by non-directive questioning of the patient at each visit during the study. Adverse events also may be detected when they are volunteered by the patient during or between visits or through physical examination, laboratory test, or other assessments. As far as possible, each adverse event should be evaluated to determine:

1. The severity grade (CTCAE Grade 1-4)
2. Its duration (Start and end dates or if continuing at the Safety Follow-up Visit)
3. Its relationship to the study treatment (Reasonable possibility that AE is related: No, Yes)
4. Action taken with respect to study or investigational treatment (none, dose adjusted, temporarily interrupted, permanently discontinued, hospitalized, unknown, not applicable)
5. Whether medication or therapy was given (no concomitant medication/non-drug therapy, concomitant medication/non-drug therapy)

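### Overall survival to 24 months is a secondary objective, but no vital-status follow-up is planned beyond about 30 days after the last dose

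*Combined protocol and SAP*

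**What the plan says.** Section 3.2 makes "Overall survival from study initiation at 6 months, 12 months, 18 months and 24 months" a secondary objective. The text on treatment and follow-up reads as follows.

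- **Treatment.** Patients are treated until progression or unacceptable toxicity. If neither occurs, section 8.7 says "treatment may continue for 2 years or until progression or non-tolerance". The calendar in section 8.5 runs to cycle 24 of 28 days.
- **Follow-up after the last dose.** Section 8.7: "Patients will be followed for evaluation of safety for at least 30 days after the last dose of study drug". Section 7.4 sets the same 30 days for all patients. Footnote g of the calendar: "Thirty day follow up to occur after last dose of study drug. Used for either end of treatment or study completion". The calendar has no vital-status row and no later column.
- **Reporting of deaths.** Section 12.2: "All deaths during treatment or within 30 days following completion of active protocol therapy must be reported within 24 hours", and "Serious adverse events occurring more than 4 weeks after study discontinuation need only be reported if a relationship to the Novartis study drug" is suspected.
- **Longer contact.** Section 13: "Adverse event monitoring should be continued for at least 30 days (or 5 half-lives, whichever is longer) following the last dose of study treatment". Section 7.4 follows patients with an adverse event or abnormal laboratory value until it resolves or stabilises. For symptomatic deterioration, section 11.3 says "Every effort should be made to document the objective progression even after discontinuation of treatment".

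Section 10 does not mention overall survival. No section says what date study initiation means for an individual patient.

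**The concern.** The objective needs vital status at fixed times up to two years from the start. The planned contacts are tied to the last dose instead. Most patients in this population will stop because of progression, so planned observation ends when the risk of death rises.

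Two things follow. First, run as written, the trial does not gather what its later landmarks need, and no choice of estimator makes up for that. Second, whatever is gathered will be selective. If patients are censored at their last planned contact, censoring follows progression, is informative, and pushes estimated survival up. If instead the site hears of later deaths informally while survivors stay censored at 30 days, the late estimates can be pushed down. With no censoring rule written, a reader of the results could not tell which had happened.

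**Working it through.** The plan gives no rate, event count, power or method for overall survival, so there is no figure of its own to reproduce. The check is calendar arithmetic, then a simulation to show scale.

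**1. Calendar arithmetic (no assumptions beyond undelayed cycles; 1 month = 365.25/12 = 30.44 days).** Last planned contact = last dose + 30 days.

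- Stop after 2 cycles: 2 × 28 + 30 = day 86 (2.8 months), before the 6-month landmark.
- Complete all 24 cycles: 24 × 28 + 30 = 672 + 30 = day 702 (23.1 months). Month 24 is day 730.5, so the shortfall is about 28 days.
- Treat for the two years in section 8.7: about 730 + 30 = day 760, past month 24.

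The calendar and section 8.7 therefore disagree on whether the last landmark can be observed at all, and they must be reconciled. Treatment needed for planned contact to reach each landmark, (landmark in days − 30)/28:

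| Landmark | Days on treatment | Cycles |
|---|---|---|
| 6 months | 182.6 − 30 = 152.6 | 5.5 |
| 12 months | 365.25 − 30 = 335.25 | 12.0 |
| 18 months | 547.9 − 30 = 517.9 | 18.5 |
| 24 months | 730.5 − 30 = 700.5 | 25.0 |

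**2. Longer contacts.** Section 2.2 gives tamoxifen a half-life of 5 to 7 days, so 5 half-lives is 25 to 35 days. Follow-up of unresolved adverse events covers only patients who have them and ends at resolution or stabilisation. Section 11.3 concerns progression and sets no schedule.

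**3. Patients still under planned contact.** With exponential time on treatment of median m (assumed, since the documents give none), the expected number of 40 is 40 × exp(−ln 2 × (L − 30 days)/m). For m = 6 months at 12 months: 40 × exp(−0.693 × 335.25/182.6) = 11.2.

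| Assumed median | 6 mo | 12 mo | 18 mo | 24 mo |
|---|---|---|---|---|
| 4 months | 16.8 | 5.9 | 2.1 | 0.7 |
| 6 months | 22.4 | 11.2 | 5.6 | 2.8 |
| 12 months | 29.9 | 21.2 | 15.0 | 10.6 |
| 18 months | 33.0 | 26.2 | 20.8 | 16.5 |

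The 24-month column supposes that treatment can run past cycle 24.

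**4. Effect on the estimate.** Simulated trials of 40 patients, exponential times. Death occurs before progression, or at time to progression (TTP) plus post-progression survival (PPS). Last planned contact is min(TTP, 24) + 1 month. Assumed median TTP/PPS is 4/12, 6/15 or 12/24 months, with a pre-progression death hazard of 0 or 0.01 per month. The last Kaplan-Meier value is carried forward.

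Unknown status, of 40, across the six scenarios: about 9–22 at 6 months, 17–32 at 12, 23–36 at 18, 26–37 at 24. With treatment capped at 24 cycles the last figure is 35–39.

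True survival against Kaplan-Meier with censoring at last planned contact, no pre-progression deaths:

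| TTP/PPS | 6 mo | 12 mo | 18 mo | 24 mo |
|---|---|---|---|---|
| 4/12 | 0.88 vs 0.95 | 0.69 vs 0.90 | 0.51 vs 0.86 | 0.37 vs 0.83 |
| 6/15 | 0.93 vs 0.97 | 0.79 vs 0.95 | 0.64 vs 0.92 | 0.51 vs 0.89 |
| 12/24 | 0.98 vs 0.99 | 0.91 vs 0.98 | 0.84 vs 0.97 | 0.75 vs 0.96 |

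At 24 months the bias is 46, 38 and 21 points. With the 0.01 hazard it falls to 34, 26 and 12. Over all six scenarios the upward bias is about 1–7 points at 6 months, 4–21 at 12, 8–35 at 18 and 12–46 at 24. If every later death is learned of but survivors stay censored at 30 days, the bias is about 0 to −1 points at 6 months and roughly −14 to −29 at 24.

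**The case against.** The best reply is that the protocol is silent on survival collection rather than opposed to it. Section 12.2 governs expedited safety notices to the drug supplier, and a limit there is not a limit on endpoint data. A cancer centre can look up dates of death later. Overall survival here is descriptive, in a small non-randomised study with several regimens, and no decision in the plan depends on it. The size of the bias, and even its sign, depends on invented survival inputs and a censoring rule the plan never states.

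Much of this is fair. Section 12.2 is supporting evidence only; the calendar and footnote g carry the point. Later look-up could recover many dates, but nothing in the plan requires it or makes it uniform across patients. The top of the bias range should be read with care. It comes from scenarios without pre-progression deaths. In the 4/12 scenario fewer than one of 40 patients remains at risk at 24 months, so carrying the last value forward contributes; a large-sample run gives 44 rather than 46 points, and about 32 rather than 34 with pre-progression deaths. The 35–39 figure counts patients last seen alive at day 702 as unknown at day 730, which adds about 8 to 11 patients in the 12/24 scenario and disappears if treatment runs two full years.

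Front matter was removed, no section 6 heading is visible and some text is blacked out, so the finding covers the available text. There, every follow-up statement agrees. None of the objections supplies a planned survival contact.

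**Conclusion.** The concern holds. The plan commits to survival at four landmarks and schedules no contact that would supply it for patients who stop early. The calendar arithmetic rests only on the stated cycle length and the 30-day visit. The counts of unknown status and the bias rest on assumed survival times and, for the bias, on an assumed censoring rule; they show scale, not a forecast. Even the mildest scenario leaves about 26 of 40 patients unknown and a 12-point upward bias at 24 months. At 6 months the bias is small, 1 to 7 points. The consequence is confined to this secondary objective.

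**What to change.** Add to the section 8.5 calendar a vital-status check for all treated patients, whatever the reason for stopping, by chart, telephone or public record. It should be periodic, or at minimum one check at 24 months from the patient's own start, and continue until 24 months, death or withdrawal of consent. In section 3.2 replace study initiation with a per-patient origin such as cycle 1 day 1. In section 10 name the estimator (for example Kaplan-Meier with confidence intervals at each landmark), set a data cut-off, and censor at the last date known alive, by the same rule for everyone. Reconcile the two-year wording of section 8.7 with the 24-cycle calendar. If the follow-up is not wanted, delete overall survival from section 3.2.

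The cost is protocol wording and one to a few record checks or calls per patient, in a study of 40 planned at one centre. It adds no visits or procedures and does not change the sample size.
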